### 5.4 Analysis Plan for Secondary Objectives

In addition to HAQ DI score, the effect of adalimumab will also be assessed by the secondary outcome measures which are changes to the Short Form 36-Item Health Survey (SF-36) domain scores, EuroQol 5 dimension 3 level (EQ-5D-3L) index, WPAI outcomes, and Patient Treatment Satisfaction Questions at 12 and 24 weeks after the initiation of adalimumab in RA.

- As to the Short Form 36-Item Health Survey (SF-36) domain scores, the Excel Table 4 summarizes the changes in PCS T-score and MCS T-score at 12 and 24 weeks after the initiation of adalimumab; these changes will be summarized as the mean, SD, minimum, maximum, median, Q1, Q3; and the mean or median change will be tested with paired t-tests or paired Wilcoxon signed-rank test .
- As to the EuroQol 5 dimension 3 level quality of life questionnaire, the Excel Table 5 summarizes the changes in EQ-5D-3L index at 12 and 24 weeks after the initiation of adalimumab; these changes will be summarized as the mean, SD, minimum, maximum, median, Q1, Q3; and the mean or median change

will be tested with paired t-tests or paired Wilcoxon signed-rank test .

- As to the WPAI outcomes, the Excel Table 6 summarizes the changes in percent overall work impairment and percent activity impairment at 12 and 24 weeks after the initiation of adalimumab; these changes will be summarized as the mean, SD, minimum, maximum, median, Q1, Q3; and the mean or median change will be tested with paired t-tests or paired Wilcoxon signed-rank tests.

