The HAQ DI is a patient-reported questionnaire to assess functioning impacted by RA. It includes the categories of dressing and grooming, arising, eating, walking, hygiene, reach, grip and common daily activities. It asks patients about the amount of difficulty they experience in these activities as well as the use of aids and/or devices. The HAQ also has a numeric rating scale (NRS) (13) to assess pain on a scale from 0 to 10. Self-administered by the patient, the completion time is approximately 3-4 minutes. The full version of HAQ DI is presented in **Error! Reference source not found.**

Short Form (36) Health Survey (SF-36)

The SF-36 is a patient-reported questionnaire of patient health-related QoL. It measures generic health concepts relevant across age, disease, and treatment groups. There are 36 items in total and the recall period is the last 4 weeks. The SF-36 consists of eight scaled scores, which are the weighted sums of the questions in their section. Each scale is directly transformed into a 0-100 scale. Completion time for the SF-36 is approximately

10 minutes. The full version of SF-36 is presented in **Error! Reference source not found.**

EuroQol 5 dimension, 3 level quality of life questionnaire (EQ-5D-3L)

The EQ-5D-3L measures the patient's overall health state in a descriptive system of health-related QoL states consisting of five dimensions (mobility, self-care, usual activities, pain/discomfort, and anxiety/depression) each of which can take one of three responses. The responses record three levels of severity ('no problems', 'some problems', and 'extreme problems') within a particular EQ-5D-3L dimension (14, 15). In addition, a VAS rates current health state between 0-100. The EQ-5D-3L results can be converted to health utility scores. Completion time for the EQ-5D-3L is approximately 2-3 minutes. The full version of EQ-5D-3L is presented in **Error! Reference source not found.**

Work Productivity and Activity Impairment (WPAI)

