9.7.5 Secondary Endpoint Analysis

The main secondary endpoint variable will be the change in HAQ DI at week 12 after the initiation of adalimumab.

The objective of endpoint analysis will be to demonstrate that treatment with adalimumab improves functioning as measured by HAQ DI in subjects with RA compared to baseline.

The main secondary analysis will be summarized as the mean and 95% confidence interval and will be tested with a paired t-test without adjusting for baseline disease severity. For sensitivity analysis, the mean change in HAQ DI at week 12 will be analyzed using ANOVA adjusting for baseline disease severity.

Other secondary analysis include:

- Change in other patient reported outcomes (SF-36 domain scales, EQ-5D Index, WPAI total lost productivity) at weeks 12 and 24 after the initiation of adalimumab, in those patients continuing on adalimumab. These changes will be summarized as the means and 95% confidence intervals and will be tested with paired t-tests.
- Number and percent of patients achieving a clinically meaningful improvement on the HAQ DI, as defined by a -0.22 point improvement or greater, at weeks 12 and 24 after the initiation of adalimumab, in those patients continuing on adalimumab.

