## 2.2 Secondary Objectives

- To describe the change in HAQ DI score at 12 weeks after the initiation of adalimumab, in those patients continuing on adalimumab (as observed population). This change will be summarized as the mean and 95% confidence interval or median (Q1,Q3) and will be tested with a paired t-test or a paired Wilcoxon signed-rank test without adjusting for baseline disease severity. For sensitivity analysis, the mean change in HAQ DI at Week 12 will be analyzed using ANCOVA adjusting for baseline disease severity.
- To describe the change in other patient reported outcomes (SF-36 domain scales, EQ-5D-3L index, WPAI total lost productivity) at weeks 12 and 24 after the initiation of adalimumab, in those patients continuing on adalimumab (as observed population). These changes will be summarized as the means and 95% confidence intervals or median (Q1,Q3) and will be tested with paired t-tests or paired Wilcoxon signed-rank tests.
- To summarize the number and percent of patients achieving a clinically meaningful improvement on the HAQ DI, as defined by a -0.22 point improvement or greater, at weeks 12 and 24 after the initiation of adalimumab, in those patients continuing on adalimumab (as observed population).

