### **Step 5: Transforming health domain scale 0-100 scores to T scores using health domain z scores**

The advantages of standardizing the health domain scales and converting 0-100 scores to norm-based scores using a T-score transformation are that health domain scale results can be meaningfully compared with each other and that these scores have a direct interpretation in relation to the distribution of scores in the 2009 US general population.

The first step is to convert the 0-100 scores into a linear z-score. A z-score would ensure each health domain scale has a mean of 0 and a standard deviation of 1 in the 2009 US general population. A z-score is computed by subtracting each health domain scale's 2009 US general population mean from the 0-100 score for that scale, and dividing the difference

by the given scale's standard deviation. Thus, the following formula is applied to convert 0-100 scores into z-scores:

$$Z\text{-score} = \frac{([0-100\text{ score}] - [83.29094])}{(23.75883)}$$

Z-scores are then transformed into T-scores (mean = 50, SD = 10) using the following formula:

$$T\text{-Score} = 50 + (z - \text{score} \times 10)$$

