### **Step 6: Scoring the physical and mental component summary measures using health domain z scores**

The Physical Component Summary (PCS) and Mental Component Summary (MCS) measures are then scored using a three-step procedure, regardless of whether a standard or acute form was administered. First, the eight health domain scales are standardized using means and standard deviations from the 2009 U.S. general population. Second, these standardized scores are aggregated using weights (factor score coefficients) from the 1990 US general population. Computation of an aggregate physical component score consists of multiplying each health domain scale z-score by its respective physical factor score coefficient and then summing the eight products. Similarly, an aggregate mental component score is obtained by multiplying each health domain scale z-score by its respective mental factor score coefficient and summing the eight products. To illustrate, a portion of the formula for aggregating scales when estimating a standard form of aggregate mental component score is as follows:

$$\text{Aggregate mental component score} =$$

$$(PF\ z - \text{score} \times -0.22999) \dots + (MH\ z - \text{score} \times 0.48581)$$

Third, aggregate PCS and MCS scores are standardized using a linear T-score transformation with a mean of 50 and a standard deviation of 10. The formulas for computing the norm-based T score for each component summary measure are:

$$PCS\ T\text{-score} = 50 + (\text{Aggregate physical component score} \times 10)$$

$$MCS\ T\text{-score} = 50 + (\text{Aggregate mental component score} \times 10)$$

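### SAP 5.4 specifies change-from-baseline analysis only for the SF-36 component summaries, while the protocol, SAP 2.2 and the title of Table 4 name the SF-36 domain scales

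*SAP*

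**What the plan says.** **Protocol.** Section 9.7.5 lists among the secondary analyses "Change in other patient reported outcomes (SF-36 domain scales, EQ-5D Index, WPAI total lost productivity) at weeks 12 and 24", to be summarised by means and 95% confidence intervals and tested with paired t-tests. The Abstract and sections 9.1 and 9.3 name the same SF-36 endpoint. Section 9.2.4.7 describes the instrument: "The SF-36 consists of eight scaled scores", each on a 0-100 scale. The physical and mental component summaries (PCS and MCS) are not named as endpoints in the protocol.

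**SAP, objectives.** Section 2.2 repeats the endpoint: "To describe the change in other patient reported outcomes (SF-36 domain scales, EQ-5D-3L index, WPAI total lost productivity) at weeks 12 and 24". It allows mean with 95% confidence interval, or median with quartiles, and says the changes "will be tested with paired t-tests or paired Wilcoxon signed-rank tests".

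**SAP, analysis.** The opening sentence of section 5.4 again names the domain scores. The one SF-36 bullet beneath it then says "the Excel Table 4 summarizes the changes in PCS T-score and MCS T-score" at both visits, and the summary statistics and paired tests that follow refer to those two scores. Section 6 titles the same Table 4 as change in the domain scales.

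**SAP, scoring.** Section 3.5.1 derives the eight domain scores in Steps 3 to 5 and builds PCS and MCS from them in Step 6.

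**The concern.** A programmer works from the analysis section. Following the 5.4 bullet, that person would fill a table titled for domain scales with two composites that the protocol does not list. The secondary result that the protocol promises, mean change in each domain, would not be produced.

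The composites do not carry the same information. Each is a weighted sum of all eight domain z-scores, so a reader cannot recover from PCS and MCS which domains changed, or by how much.

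While the SAP says two things, the choice of which SF-36 results to report as secondary stays open. The document history lists edits to sections 2 and 5 in V0.2, V0.3 and V0.4, and none of them explains a move from domains to summaries.

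**Working it through.** No power or sample-size figure is at issue. The check compares the text, counts the results, and looks at two side questions.

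**1. What each place names as the SF-36 outcome**

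| Place | SF-36 outcome for change from baseline |
|---|---|
| Protocol Abstract, 9.1, 9.3, 9.7.5 | Domain scales |
| SAP 2.2 | Domain scales |
| SAP 5.4, opening sentence | Domain scores |
| SAP 5.4, SF-36 bullet | PCS and MCS T-scores |
| SAP section 6, title of Table 4 | Domain scales |

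The bullet is alone, but it is the only place in the SAP's analysis section that says which SF-36 scores are summarised and tested for change.

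**2. Count of change-from-baseline results**

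- Protocol and SAP 2.2: 8 domains x 2 visits = 16.
- SAP 5.4 bullet: 2 summaries x 2 visits = 4, none on a domain scale.
- Both kept: 16 + 4 = 20.

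**3. Where else the domain scales appear**

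SAP 5.5 relates the domain scales to DAS28 (Table 10.1) and the change in each patient-reported outcome to the change in DAS28 (Table 10.2). Table 11 models effect modification for changes in the secondary outcomes. All are listed as exploratory in SAP 2.3. A slope or a correlation with DAS28 does not estimate or test the mean change in a domain, so these tables do not supply the secondary result.

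**4. How far a summary can depart from the domains**

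Step 6 introduces the MCS weights with "a portion of the formula for aggregating scales when estimating a standard form of aggregate mental component score is as follows", and prints two of eight: physical functioning -0.22999 and mental health +0.48581. The MCS T-score is 50 + 10 x aggregate.

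- Physical functioning up 1 z-unit, all other domains fixed: 10 x (-0.22999) = -2.3 points.
- Physical functioning and mental health both up 1 z-unit, the other six fixed: 10 x (0.48581 - 0.22999) = +2.6 points.

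The sign of the net effect therefore depends on how the domains move together and on six weights that the SAP does not print.

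**5. The constants in Step 5**

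Step 5 says each scale is standardised with its own population mean and SD. It then says "Thus, the following formula is applied to convert 0-100 scores into z-scores" and prints one unlabelled pair, 83.29094 and 23.75883. If that pair were used for every domain, the mean would cancel in a change score but the SD would not: each T-score change would be 10 / 23.75883 = 0.421 times the 0-100 change. A single domain's paired t-test would not alter, because the rescaling is by a constant. The size of the T-score change would alter, and so would PCS and MCS.

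**6. Multiplicity, for context**

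Protocol 9.7.3 sets a two-sided 0.05 for all tests. If the tests were independent and all nulls true, the chance of at least one false positive is 1 - 0.95^k:

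- k = 4: 18.5%
- k = 16: 56.0%
- k = 20: 64.2%

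Independence is an assumption. The scales are correlated, so these figures are only a guide to why the status of the p-values should be stated.

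**The case against.** The strongest reply is that this is one inconsistent bullet and not a dropped endpoint. SAP 2.2 still commits to testing the domain changes, the opening of 5.4 and the title of Table 4 agree with it, and nothing says that 5.4 overrides 2.2. Protocol 9.7.1 allows the SAP to add analyses, so PCS and MCS could be meant as additions. The rows of Table 4 sit in a separate workbook that was not supplied and may already list the domains. All of this stands. It rules out the claim, which a reader might infer from 5.4 alone, that the domain scales are never analysed. It does not remove the contradiction.

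A reader might also infer that a gain in physical functioning mechanically lowers MCS and so hides mental improvement. The documents support only the partial effect, with the other domains held fixed. The printed mental health weight is positive and about twice as large.

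On Step 5, it is tempting to read the single pair as constants for all eight scales. The surrounding text says each scale has its own, and section 3.5.1 ties scoring to the developer's recommendations. The pair is most naturally an unlabelled example, so this is a labelling note and adds no weight to the main point.

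Finally, V0.4 records replacing the confidence interval of the mean by quartiles because normality was violated, so a request for intervals might seem to reverse a decision. SAP 2.2 still provides for mean and 95% confidence interval, and quartiles describe the spread of individual changes, not the precision of the mean. Reporting both where normality fails respects that decision and the protocol.

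**Conclusion.** The point holds as an internal contradiction on a pre-specified secondary endpoint. Taken literally, the SF-36 bullet in SAP 5.4 yields 4 composite results and none of the 16 domain results that the protocol and SAP 2.2 call for, and no rationale is recorded. The exploratory association models do not fill the gap.

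This rests on reading the 5.4 bullet as the working instruction for Table 4. If the unseen shell already holds the eight domains, the defect is confined to the wording of 5.4. The primary endpoint is unaffected. The matter should be corrected because the secondary SF-36 result is at stake and the remedy is simple.

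**What to change.** - **SAP 5.4 and the Table 4 shell:** list the change in all eight domain scales at weeks 12 and 24 as the secondary SF-36 analysis. Give mean and 95% confidence interval, as in the protocol and SAP 2.2, and add median, Q1 and Q3 where normality fails.
- **Metric:** say whether domain changes are reported on the 0-100 scale (Protocol 9.2.4.7) or as T-scores (SAP Step 5).
- **PCS and MCS:** keep them in the table, labelled supplementary.
- **p-values:** state that they are nominal, with no multiplicity adjustment.
- **Document history:** record the correction.
- **Minor, Step 5:** label the printed mean and SD as an example for one named domain, or print all eight pairs.

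The cost is a revised bullet, a few sentences, and rows for eight domains at two visits in an existing table. The domain scores are already derived in Steps 3 to 5 on the way to PCS and MCS, so no new data are needed.

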## 5.5 Analysis Plan for Exploratory Objectives

- Excel Table 7 describes the change in 4 patient satisfaction questions at weeks 12 and 24 after the initiation of adalimumab, in those patients continuing on adalimumab (observed population). These changes will be summarized as number and percentage of each response and compared with Wilcoxon signed rank test. Satisfaction will also be dichotomized and analyzed over time with Cochran-Armitage test for trends.
- Excel Table 8 summarizes the patients' global impression of change in RA at weeks 12 and 24 after the initiation of adalimumab, in those patients continuing on adalimumab (as observed population). Each response (very much better, much better, a little better, no change, a little worse, much worse, and very much worse) will be summarized as number and percentage.
- Descriptive statistics will be presented for post-index overall RA related direct healthcare resource utilization (Excel Table 9)
  - Consultations/visits to healthcare professionals for treatment of RA (number of patients with  $\geq 1$  visit; categorized by the treatment department listed in 3.5.4)
  - Procedures received when visiting the healthcare professional(s) for treatment of RA (number of patients with  $\geq 1$  procedure; categories listed in 3.5.4)
  - surgeries received when visiting the healthcare professional(s) for treatment of RA (number of patients with  $\geq 1$  surgery; categories listed in 3.5.4)
  - Hospitalizations in relation to RA (number of patients with  $\geq 1$  admission)
  - Length of stay in days (mean, SD, median)
  - Concomitant medications taken for RA (number of patients with  $\geq 1$  medication; categories listed in 3.5.4))

- Associations between disease severity (measured by DAS28) and PROs (HAQ DI score, SF-36 domain scales, EQ-5D-3L index, WPAI outcomes) will be analyzed using the bivariate linear regression model (Excel Table 10.1). Separate models will be estimated to identify the association between DAS28 and each of the PROs. If normality assumption for the residual of regression is violated, Spearman correlation coefficients and p-values will be estimated instead.
- Additionally, in Excel Table 10.2, separate bivariate linear regression models will be estimated to identify the association between change in DAS28 and change in each of the PROs at 12 and 24 weeks after baseline respectively. If normality assumption for the residual of regression is violated, Spearman correlation coefficients and p-values will be estimated instead.
- In Excel Table 11, separate multivariate generalized linear models (GLM) will be estimated to test for the differential changes in primary and secondary efficacy outcomes after baseline, across the subgroups defined by the potential modifiers, including age, gender, baseline severity, and other diagnoses/comorbidities.

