4.0 Abstract

Title: Real-World Outcome of Adalimumab on Rheumatoid Arthritis Patients in China

Rationale and Background: Given the requirement to keep a balance between effectiveness and cost containment to ensure that the available health resources are used in a cost-effective manner, there is an increasing demand for real-world evidence (RWE) from policy makers, regulators, providers and payers in the region to optimize spending and patient outcomes.

So far, there are no data available regarding adalimumab's impact on patients' quality of life (QoL) and healthcare resource utilization (HCRU) in a realistic study design, which provides greater generalization in China.

The goal of this study is to determine the QoL, HCRU and costs of the patients care in subjects with RA who are treated with adalimumab in China.

Results from study on the effect of adalimumab on Work Productivity and Activity Impairment (WPAI) scores and other Patient-Reported Outcomes (PROs) will be of interest to a variety of stakeholders in the healthcare system including patients, healthcare practitioners and payers in China.

Research Question and Objectives: The objective of this non-interventional, observational study is to assess the effect of adalimumab on health-related QoL and work productivity in patients with Rheumatoid Arthritis (RA) in China. Specifically, to achieve the above objective the following concrete steps will be taken:

1. Recruit investigators who are willing and able to recruit and follow new adalimumab users for 6 months follow-up
2. Collect the patients' clinical profile, patient-reported QoL, functioning, work productivity, treatment satisfaction and HCRU of RA patients at adalimumab initiation
3. Follow the patients initiating adalimumab for 24 weeks and identify the changes in clinical, economic, and PROs associated with adalimumab

Study Design: The study is designed as a prospective, observational study to assess the effect of adalimumab on health-related QoL and work productivity in patients with RA in China.

RA patients, for whom adalimumab treatment has already been decided as per local label, will be recruited from within the clinical settings of each rheumatologist participating in the study. Approximately 52 patients diagnosed with RA that meet the inclusion and exclusion criteria will be enrolled at approximately 16 sites.

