9.1.1 Study Activities

Table 1 Study Activities (Day 1/Baseline Through 6 months)

	Data Collection/Observation	Baseline ^a	Week 12 (V2) ± 7 days	Week 24 (V3) ± 7 days	Early Termination / Drop out	70 days after the Week 24 or the last dose	150 days after the Week 24 or the last dose
Clinician Packet	Inclusion/exclusion form	X					
	Clinical history/patient demographics	X					
	Comorbidities	X					
	DAS28 (ESR) or DAS28 (CRP)	X	X	X	X		
Patient Packet	EuroQoL 5-Dimension (EQ-5D)	X	X	X	X		
	Short Form 36-Item Health Survey (SF-36)	X	X	X	X		
	Health Assessment Questionnaire (HAQ)	X	X	X	X		
	Work Productivity and Activity Impairment Questionnaire (WPAI)	X	X	X	X		
	Healthcare Resource Utilization (HCRU)	X	X	X	X		
	Patient Global Impression of Change (PGIC)		X	X	X		
	Patient Treatment Satisfaction Questions	X	X	X	X		
Clinical n	Adverse events (including malignancy)	←				→	
	Pregnancy	←					→

a. The Baseline visit date will serve as the reference for all subsequent visits. A \pm 7 day window is permitted around scheduled study visits.

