The WPAI is a patient-reported questionnaire to measure work and activity impairment during the past seven days. It determines employment status, hours missed from work due to the disease (i.e. RA), hours missed from work for other reasons, hours actually worked, the degree to which the disease affected work productivity while at work and the degree to which the disease affected activities outside of work. Additional questions around employment status will be incorporated into the survey. The completion time for the WPAI is approximately 2-5 minutes. The full version of WPAI is presented in **Error! Reference source not found.**

All of the above questionnaires will be used with the validated Chinese version.

Patient Global Impression of Change (PGIC)

The PGIC measures the patient's perceptions of changes in their disease. It consists of one question asking about the change in their condition; for this study, the base will be "since you initiated your adalimumab treatment". The completion time for the PGIC is less than 1 minute. The full version of PGIC is presented in **Error! Reference source not found.**

Patient Treatment Satisfaction Questions

The patient treatment satisfaction questions were developed de novo for this study and are not considered "validated" questions. Self-administered by the patient, the completion time for the patient treatment satisfaction questions is approximately 1-2 minutes. The full version of patient treatment satisfaction questions are presented in **Error! Reference source not found.**

Healthcare Resource Utilization (HCRU) Questionnaire

The HCRU questionnaire will collect data on the healthcare resources consumed in the prior 3 months, as recall beyond 3 months may be problematic in an older population (16). HCRU collection will include data such as the number of physician visits and to which physician (GP, specialist), Emergency Department visits, hospitalizations, and other drugs as well as devices and aids purchased to assist in their mobility due to RA. The HCRU questionnaire will be part of the patient questionnaire and will be distributed to patients together with the PRO questionnaires (Appendix D to Appendix I). The full HCRU questionnaire is presented in **Error! Reference source not found.J** and will be used with the validated Chinese version.

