9.3 Variables

Variables:

Primary Variable

- Change in HAQ DI score at week 24 from the baseline

Secondary Variable

- Change in HAQ DI score at week 12 from the baseline
- Change in other PROs (SF-36 domain scales, EQ-5D Index, Work Productivity and Activity Impairment Questionnaire [WPAI]) from baseline to weeks 12 and 24
- Number and percent of patients achieving a clinically meaningful improvement on the HAQ DI, from baseline to weeks 12 and 24

Additional Secondary Variable

- Change in HAQ DI score from baseline to week 24
- Changes in the disease severity and PROs from baseline to week 24
- Healthcare Resource Utilization (HCRU) at baseline, weeks 12 and 24

Exploratory Variable

- Change in patient satisfaction questions from baseline to weeks 12 and 24
- Patient's impression of change at weeks 12 and 24 from baseline

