On August 30th, 2012, National Development and Reform Commission (NDRC), Ministry of Health (MOH) and other four ministries and commissions of China issued “Guidance about implementation of urban and rural residents’ critical disease insurance (CDI) system” . The CDI system aims to expand the coverage of the country’s health care insurance system to include the treatment of critical illness, aiming to relieve urban and rural families of the heavy burden of catastrophic medical spending. By the end of August 2013, 94 regions across 23 provinces had piloted the critical illness cover system and seven provinces had fully implemented the system, benefiting 210 million people.

In Jan 2015, Humira was listed on the CDI in Qingdao. Patients with RA who are covered by CDI are reimbursed for 70 percent of the total costs. Given CDI is a new system in China, the Qingdao officials encourage companies to collect the RWE associated with the use of Humira to further demonstrate the value of Humira to patients. The result will assist decision makers to evaluate the CDI from a broader perspective and to determine the value of continuing the program.

In addition, generating RWE related with the use of Humira in patients with RA will be extremely valuable for application of Humira on the CDI list in other provinces in China. The successful applications in other provinces will ensure more patients with RA in China will be able to access the Humira.

The objective of this non-interventional, observational study is to assess the effect of adalimumab on health-related QoL, work productivity, and healthcare resource utilization (HCRU) in patients with RA in China.

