### **3.5 Definitions of Study Variables**

The key variables of interest in this study are demographic and clinical characteristics, patient-reported health and disability outcomes, and healthcare resource utilizations. Most variables will be measured at baseline (i.e. index), and at weeks 12 and 24 after

the initiation of Adalimumab; healthcare resource utilization will be summarized over the 6 month post-index period.

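### The SAP reports healthcare resource use only after the index date, so the planned analysis omits the baseline time point listed in Protocol 9.3 and has no comparator

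*SAP*

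**What the plan says.** **Collection.** Protocol 9.3 names as an additional secondary variable "Healthcare Resource Utilization (HCRU) at baseline, weeks 12 and 24". Table 1 in Protocol 9.1.1 schedules the HCRU questionnaire at baseline, week 12, week 24 and early termination. SAP 3.1 also has patients completing HCRU forms at baseline, week 12 and week 24. On recall, Protocol 9.2.4.7 states: "The HCRU questionnaire will collect data on the healthcare resources consumed in the prior 3 months".

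**Aim.** SAP 1.1 gives the study objective as to "assess the effect of adalimumab on health-related QoL, work productivity, and healthcare resource utilization (HCRU) in patients with RA in China", and Protocol 7.0 says the same. The Protocol abstract adds that patients will be followed to "identify the changes in clinical, economic, and PROs associated with adalimumab".

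**Analysis.** SAP 3.5 says that most variables are measured at all three times, but that "healthcare resource utilization will be summarized over the 6 month post-index period". SAP 5.5 then specifies: "Descriptive statistics will be presented for post-index overall RA related direct healthcare resource utilization (Excel Table 9"). The list in SAP 6 has one HCRU table, Table 9, and its title limits it to post-index use. The baseline characteristics in SAP 5.2 (Tables 1 and 2) contain no HCRU item.

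**The concern.** The baseline form covers the 3 months before adalimumab, a window of the same nominal length as each follow-up form. In a single-arm study it is the only internal comparator for resource use. The SAP gives no analysis of it and no reason for leaving it out.

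HCRU is alone in this. Every other patient questionnaire with a scheduled baseline (HAQ DI, SF-36, EQ-5D-3L, WPAI, treatment satisfaction) has a change table in SAP 6. The global impression of change has none because it has no baseline assessment. Both documents also exclude patients who could not accurately report their prior resource use, so the design takes care to obtain data that the analysis then ignores.

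Protocol 7.0 and SAP 1.1 say the results are meant to help decision makers judge critical-illness insurance coverage of the drug. A post-only table tells them how much care was used, but not whether that was more or less than before.

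**Working it through.** The point rests on setting the texts side by side. The documents give no HCRU figure to reproduce.

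**1. Time points.**
- Listed in Protocol 9.3: baseline, week 12, week 24.
- Reported in SAP 3.5, 5.5 and 6: post-index only.
- Unused: baseline, one of three windows. No section of either document plans a baseline HCRU summary or a comparison with it.

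**2. Why a baseline column beside the present Table 9 is not enough.** Let p be the probability of at least one use in 3 months, assumed constant and independent between quarters. Over 6 months the probability is 1 − (1 − p)². With no true change:

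| Assumed p (3 months) | 6 months |
|---|---|
| 5% | 9.8% |
| 10% | 19% |
| 20% | 1 − 0.8² = 36% |
| 30% | 51% |
| 50% | 75% |

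A 3-month baseline beside a 6-month follow-up figure would therefore show a false rise. If the same patients tend to use care in both quarters the rise is smaller, but the windows still do not match.

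**3. Recall overlap.** Take 3 months as about 13 weeks, with visits at weeks 12 and 24. The week-12 form reaches back to week −1, and the week-24 form to week 11. One week is covered twice and one week lies before baseline.
- Summed quantities, if the two forms are added: 26/24 = 1.083. With the ±7-day window at week 24, follow-up is 23 to 25 weeks, giving 26/25 = 1.04 to 26/23 = 1.13. In SAP 5.5 this can touch only length of stay.
- Items reported as patients with at least one use: double recall changes nothing. Only the week before baseline matters. The two forms together span 25 weeks against 24, and 25/24 = 1.042, so at most about 4% in relative terms for rare, evenly spread events.

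**4. What a paired difference can show.** Protocol 9.5 plans 52 patients with 10% dropout: 52 × 0.9 = 46.8, about 47 pairs if every form is completed. Let b and c be the proportions changing in each direction. The 95% half-width is 1.96 × √[(b + c − (b − c)²)/47]. For assumed values:
- b = 10%, c = 2%: difference 8 points, ± 9.6
- b = 20%, c = 5%: difference 15 points, ± 13.6
- b = 30%, c = 10%: difference 20 points, ± 17.2

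The intervals will be wide, but they are informative enough for a description.

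**The case against.** The strongest reply is that HCRU was never set up as a change endpoint. Protocol 9.3 uses the word change for other variables but not for HCRU. Protocol 9.7.6 only describes it, and SAP 2.3 treats it as exploratory and only summarizes it. The sentence about an effect on HCRU stands in the background sections, while Protocol 8.0 and SAP 2 do not mention HCRU. This stands: a reader might infer that the SAP removed a planned change analysis, and the documents do not support that. What the SAP does drop is the listed baseline time point. The lack of any comparison is a gap against the stated aims in both documents.

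The second reply is that baseline is not a clean comparator. Eligibility depends on a laboratory profile, chest x-ray, ECG and TB screening (Protocol 9.2.1). SAP 3.2.1 allows up to 90 days for the first three, which is about the baseline recall period. SAP 3.5.4 counts chest x-ray, ECG, blood samples and tuberculin tests as procedures. Patients also enter with DAS28 above 3.2, so some regression to the mean is likely. This stands too, and it calls for a caveat rather than for omitting the window.

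Third, a reader might infer a general over-count of about 8% from overlapping recall. The documents do not support that. SAP 5.5 reports everything except length of stay as patients with at least one use, which double recall cannot inflate. Pooling is itself an inference from the 6-month wording: no section says how the two forms are combined, and the table shells are a separate file.

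**Conclusion.** The point holds in limited form. The SAP leaves out a time point that the protocol lists and schedules, and with it the only comparator for a stated aim. The planned HCRU analysis therefore cannot show the direction of any change. This affects one exploratory, descriptive table and leaves the primary endpoint and the sample size untouched.

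It would go too far to say that the study itself cannot show a change. The baseline forms are scheduled, so the limit lies in the planned analysis and not in the design, although Protocol 9.1 collects HCRU only when available. It would also go too far to expect the repaired analysis to establish a drug effect: this is a single-arm before-and-after comparison.

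The conclusion assumes that Table 9 follows its title and SAP 3.5. The 36% illustration assumes constant, independent quarters.

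**What to change.** In SAP 3.5, 5.5 and Table 9:

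- Report HCRU descriptively for each 3-month window separately (baseline, week 12, week 24), each with its own denominator. Protocol 12.6 lets a patient miss week 12 and still complete week 24, and SAP 3.5.5 does not impute missing forms, so a combined 6-month figure has no clear denominator.
- Add the within-patient difference from baseline with a 95% CI for the main categories only: any consultation, any procedure, any surgery, any hospitalization, and bed days. Label these exploratory.
- Do not add McNemar tests for every item. SAP 3.5.4 lists 9 departments, 17 procedures and 9 surgeries. At two time points that is (9 + 17 + 9) × 2 = 70 tests before medications, in about 52 patients and with no multiplicity plan.
- Do not place a pooled 6-month figure beside the 3-month baseline, and do not sum bed days across overlapping recalls.
- Footnote that baseline procedures may include the eligibility work-up, that the week-12 form may reach about a week before baseline, that patients entered with active disease, and that a single-arm change does not prove a drug effect.
- Say how the early-termination form is handled, since Table 1 schedules HCRU there as well.

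The cost is a somewhat larger table and some programming. No new data collection is needed, though baseline forms may be missing for some patients and the number available should be shown.
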